The primary endpoint is the pharyngeal cure rate – that is, the proportion of subjects who return for TOC who clear their infections as evidenced by a negative culture 4-7 (+/-1) days after treatment. Persons who test negative for NG at their enrollment visit (i.e. infection cleared between initial clinical screening test and enrollment) will be excluded from analysis. Treatment failure will be defined as a positive culture 4-7 (+/-1) days after treatment. The cure rate will be calculated as the number of cured subjects divided by the total number of subjects who received treatment and returned for follow-up testing in a modified an intention to treat (mITT) analysis. We will also calculate the 95% CI for this proportion.

We will conduct an interim analysis after we have primary outcome results for 25 subjects. If the cure rate is $\leq 44\%$ (99% CI 17% – 74%; i.e. 12 persons of 25 persons with a positive culture on treatment date fail treatment), we will stop the study. We will also monitor for renal toxicity at the interim analysis. We plan to obtain pre-treatment and post-treatment Creatinine. Increases $>40\%$ will be considered significant. If more than 20% of the study population has a $>40\%$ increase in serum Creatinine, we will halt the study. We chose 20% because if 20% of subjects experience renal toxicity it is unlikely to be due to chance (95% CI 7 – 40%). For our second objective, we will compare the MIC of cures to treatment failures using a stratified approach (Table 2), and we will correlate this data with individual peak gentamicin level in order to estimate the ideal pharmacodynamic (PD) criterion (Obj. 2). For persons who fail treatment we will also compare the pre- and post-treatment genatmicin MIC to estimate whether single dose gentamicin therapy can “induce” resistance (Obj. 3) as an exploratory analysis. We will consider an increase in the MIC by two doubling-dilutions (i.e. from MIC of 2 to 8 $\mu\text{g/mL}$, or 8 to 32 $\mu\text{g/mL}$) to represent induced resistance, and we will calculate the

proportion of isolates among those that fail treatment that demonstrate induced resistance following receipt of gentamicin. Lastly, we will report the number and proportion of subjects who report side effects.

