The NRL first determines cefixime, ceftriaxone and azithromycin MIC by the etest method initially for prompt clinical action. Then, gonorrhea isolates undergo AST according to the Clinical and Laboratory Standards Institute (CLSI) recommended agar dilution method for further surveillance.[13] AST testing includes: Penicillin (PEN), Tetracycline (TET), Cefixime (CFM), Ceftriaxone (CRO), Ciprofloxacin (CIP), Azithromycin (AZM), and Gentamicin (GEN). We used CLSI[15] breakpoints to interpret MICs for penicillin ($\geq 2.0\mu\text{g/ml}$), tetracycline ($\geq 2.0\mu\text{g/ml}$), spectinomycin ($\geq 128.0\mu\text{g/ml}$), and ciprofloxacin ($\geq 1.0\mu\text{g/ml}$),[15] and used GISP alert values for azithromycin ($\geq 2.0\mu\text{g/ml}$), cefixime ($\geq 0.25\mu\text{g/ml}$), and ceftriaxone ($\geq 0.125\mu\text{g/ml}$) as CLSI has not established breakpoints for these antimicrobial agents.[12] Neither CLSI nor CDC have published breakpoints for gentamicin however, other institutes have used the following breakpoints that we will follow in this study: Resistant is $\geq 32\mu\text{g/ml}$; Intermediate susceptible 8-16 $\mu\text{g/ml}$, and Susceptible $\leq 4\mu\text{g/ml}$. Full AST results will be reported to the PI.

Data Safety and Monitoring Plan, Resolving & reporting Protocol Deviations, AEs and Unanticipated problems

OVERSIGHT RESPONSIBILITIES

Day-to-day oversight of the trial is provided by the Principal Investigator (PI), [name], along with [name] (co-I). [name] assures that informed consent is obtained prior to performing any research procedures, that all subjects meet eligibility criteria, and that the study is conducted according to the IRB-approved research plan. Drs. [name] and [name] review all study data and any adverse events (AEs) real-time, and report all SAEs to the Medical Monitor and IRB according to the approved DSMP.

Medical Monitor: Monitoring for the study will be provided by a volunteer Medical Monitor, [name], Professor of Medicine in the Division of Allergy and Infectious Diseases, who has over 25 years of experience with clinical trials, but is not directly related to the study team.

MONITORING PROCEDURES

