The Medical Monitor, [name], will review study conduct including efficacy and renal toxicity and AEs in aggregate on at a single interim analysis after 25 subjects, and at the end of the study. The Medical Monitor will review serious adverse events (SAEs), hearing loss, and serious drug allergies in real-time. Study data are provided to the Medical Monitor prior to the interim and final analysis. Data reports are prepared by the PI, [name].

MONITORING REPORT

The Medical Monitor, [name], will provide a written report to the study team with recommendations for study modification, study continuation/discontinuation as relevant. The study team is responsible for forwarding the report to the IRB.

COLLECTION AND REPORTING OF SAEs AND AEs

For this study, the following standard AE definitions are used:

Adverse event: Any unfavorable and unintended sign (including an abnormal laboratory finding), symptom or disease temporally associated with the use of a medical treatment or procedure, regardless of whether it is considered related to the medical treatment or procedure.

Serious Adverse Event: Any AE that results in any of the following outcomes:

- Death
- Life-threatening
- Event requiring inpatient hospitalization or prolongation of existing hospitalization
- Persistent or significant disability/incapacity

AEs are graded according to the following scale:

Mild: An experience that is transient, & requires no special treatment or intervention. The experience does not generally interfere with usual daily activities. This includes transient laboratory test alterations.

Moderate: An experience that is alleviated with simple therapeutic treatments. The experience impacts usual daily activities. Includes laboratory test alterations indicating injury, but without long-term risk.

Severe: An experience that requires therapeutic intervention. The experience interrupts usual daily activities. If hospitalization (or prolongation of hospitalization) is required for treatment it becomes an SAE.

The study uses the following AE attribution:

Not related: The AE is clearly not related to the study procedures (i.e., another cause of the event is most plausible and/or a clinically plausible temporal sequence is inconsistent with the onset of the event).

Possibly related: An event that follows a reasonable temporal sequence from the initiation of study procedures, but that could readily have been produced by a number of other factors.

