Related: The AE is clearly related to the study procedures.

AEs are identified at the TOC visit using the symptom screen, and with Creatinine monitoring.

SAEs and specific procedure-associated AEs are reported to the Medical Monitor within 24 hours. In addition, all AEs are reported according to the University of Washington AE reporting guidelines.

MANAGEMENT OF RISKS TO SUBJECTS

Expected AEs

Expected AEs associated with gentamicin include:

- Pain at injection site
- Bruising at injection site

AE Management

- Warm compresses as needed
- Tylenol as needed

DATA ANALYSIS PLANS

The Medical Monitor will conduct interim analyses after we have primary outcome results for 10 and 25 subjects. (Enrollment will pause until analyses can be conducted). Stopping rules include the primary end point (i.e. pharyngeal cure rate), and adverse events. If after 10 and 25 subjects, the cure rate is $\leq 44\%$ (99% CI 17% – 74%; i.e. 11 persons of 25 persons with a positive culture on treatment date fail treatment), we will stop the study. We chose these numbers using the O'Brien-Fleming method of alpha spending for multiple analyses, assuming an alpha of 0.003 for the first analysis and an alpha of 0.049 for the final analysis. Using the 99% CI obtained with 11/25 treatment failures, the upper bound is less than 75%. (Our hypothesis is that gentamicin alone will be 80% effective for pharyngeal gonorrhea, with the goal to use it in combination with a second agent). Alternatively, if at interim analysis more than 20% of subjects (99% CI 20% - 46%) have a greater than 40% increase in their creatinine from baseline, we will halt the study.

Data Analysis

The proposed study aims to evaluate the efficacy of a single intramuscular (IM) dose of 360 mg of gentamicin in the treatment of pharyngeal gonorrhea. Secondary objectives include evaluating the renal safety and tolerability of 360mg of gentamicin, *documenting peak serum gentamicin levels by subject weight*, and estimating the ideal pharmacodynamic criterion using a combination of peak gentamicin concentration levels compared to MIC and treatment outcomes. *In exploratory analyses*, we will attempt to determine whether gentamicin-monotherapy induces antimicrobial resistance among treatment failures. The specific aims are:

- 1) Determine the proportion of persons whose pharyngeal gonococcal infections are cured with a single dose of 360mg gentamicin intramuscularly alone.

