As a means to preserve funding and ensure safety, we will conduct interim analyses after we have primary outcome results for 10 and 25 subjects. (Enrollment will pause until analyses can be conducted). Stopping rules include the primary end point (i.e. pharyngeal cure rate), and adverse events. If after 25 subjects, the cure rate is $\leq 44\%$ (99% CI 17% – 74%; i.e. 11 persons of 25 persons with a positive culture on treatment date fail treatment), we will stop the study. We chose these numbers using the O'Brien-Fleming method of alpha spending for multiple analyses, assuming an alpha of 0.003 for the first analysis and an alpha of 0.049 for the final analysis. Using the 99% CI obtained with 11/25 treatment failures, the upper bound is less than 75%. Alternatively, if at interim analysis 32% or more of subjects (99% CI 9.4% - 63%) have a greater than 40% increase in their creatinine from baseline, we will halt the study.

Appendices

- A. Clinician Information and Referral Script
- B. Study Info Card
- C. Appointment Reminder Card
- D. Screening Eligibility Form
- E. Enrollment visit data entry form
- F. TOC visit data entry form

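### No rule ends enrollment once the failure count that triggers the 25-outcome efficacy stop has been reached, so subjects can be dosed after that decision is certain

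*Combined protocol and SAP*

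**What the plan says.** The document describes the efficacy look in four places, and they differ.

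- **Statistical Analysis Plan (opening Objectives section):** "We will conduct an interim analysis after we have primary outcome results for 25 subjects". The study stops at a cure rate of 44% or lower, which the text equates with 12 failures of 25.
- **Monitoring Procedures:** the Medical Monitor reviews efficacy "in aggregate on at a single interim analysis after 25 subjects, and at the end of the study".
- **Data Analysis Plans (safety monitoring section):** "The Medical Monitor will conduct interim analyses after we have primary outcome results for 10 and 25 subjects". The threshold acts at both looks ("If after 10 and 25 subjects, the cure rate is"). The failure count given is 11 of 25.
- **Data Analysis, Analyses:** "we will conduct interim analyses after we have primary outcome results for 10 and 25 subjects", but the threshold is given only at the second look ("If after 25 subjects, the cure rate is"). The failure count is again 11 of 25.

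The last two sections pause enrollment while each look is analysed. That pause is tied to the scheduled looks, not to the failure count. Under Oversight Responsibilities the study leads "review all study data and any adverse events (AEs) real-time", but no efficacy stop is attached to that review. Under Laboratory Processing, positive cultures are reported to the clinic record as they are identified.

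**The concern.** A cure-rate threshold applied to exactly 25 outcomes is a count of failures. Once that count is reached, no later outcome can reverse the decision. Anyone enrolled between the deciding failure and outcome 25 is dosed without being able to affect whether the study stops. The Data Analysis section says the interim looks exist to save funds and protect safety, and continuing past that point serves neither. The executive summary also notes that a related aminoglycoside failed at this anatomic site, so a low cure rate is a possibility the sponsor has itself raised.

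**Working it through.** **Inputs from the document.** Look at 25 outcomes, and in two sections also at 10. Stop at a cure rate of 44% or lower. Printed failure counts of 12 or 11. Hypothesised cure rate 80%. Outcome 4–7 (±1) days after dosing.

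**Assumptions.** Outcomes are independent with a common cure probability p (q = 1 − p). The 25 are evaluable outcomes. The range p = 20–50% is illustrative.

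**The plan's own figure.** 11/25 = 44% cured, so 44% or lower means at least 25 − 11 = 14 failures. The printed interval of 17%–74% is the exact interval for 11 cured of 25 at alpha 0.003 (17.1%–73.8%). At the stated 99% level the exact interval is 19.7%–70.5%. The printed counts imply other cure rates: 12 failures is 13/25 = 52% cured, and 11 failures is 14/25 = 56% cured. All three lines (F = 14, 12, 11) are carried below, without choosing between them.

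**Same decision.** There are at least F failures in 25 outcomes exactly when the F-th failure occurs at or before outcome 25. Stopping at the F-th failure therefore gives the same stop/continue result in every trial. For F = 14, 200,000 simulated trials at each of four cure rates (20, 30, 40 and 50%) agreed without exception.

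**Size, efficacy line only at 25.** The F-th failure falls at outcome n with probability C(n−1, F−1) q^F p^(n−F). Mean outcomes avoidable = sum over n = F to 25 of (25 − n) times that probability.

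| Failure line F | p = 20% | 30% | 40% | 50% | Maximum (25 − F) |
|---|---|---|---|---|---|
| 14 (44% cured) | 7.5 | 5.1 | 2.6 | 0.8 | 11 |
| 12 (Statistical Analysis Plan) | 10.0 | 7.9 | 5.2 | 2.5 | 13 |
| 11 (Data Analysis Plans; Data Analysis) | 11.2 | 9.3 | 6.8 | 3.8 | 14 |

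Check for F = 14, p = 20%: the mean time to the 14th failure is 14/0.8 = 17.5, and 25 − 17.5 = 7.5. For this line, among trials that stop, the result was already certain before outcome 25 in 99.8%, 96.9%, 88.8% and 78.4% at the four cure rates.

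**Size, 44% rule also acting at 10.** 4/10 = 40% stops and 5/10 = 50% continues. P(4 or fewer cured of 10) is 0.967, 0.850, 0.633 and 0.377 at the four cure rates, so many poorly performing trials end at 10. A trial that continues has at most 5 failures by then, so the F-th failure cannot come before outcome 10 + F − 5. Restricting the sum to paths with 5 or fewer failures in the first 10 gives:

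| Failure line F | Mean avoidable, p = 20–50% | Earliest deciding outcome | Maximum |
|---|---|---|---|
| 14 | 0.1–0.3 | 19 | 6 |
| 12 | 0.2–1.0 | 17 | 8 |
| 11 | 0.2–1.5 | 16 | 9 |

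**At p = 80%, no efficacy stop at 10.** P(stop at 25) is 0.00008, 0.0015 and 0.0056 for F = 14, 12 and 11, with or without curtailment. The saving is essentially nil.

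**The case against.** A fixed-size look is a standard and valid design, and the second look does more than judge efficacy. It also covers renal toxicity, and every subject dosed adds to the renal, pharmacokinetic and MIC aims. Aggregate review by a Medical Monitor outside the study team could be displaced by a running efficacy tally kept by investigators. The saving is small in plausible cases: under one outcome on average with the 14-failure line if the rule acts at 10, and 0.8 at 50% true cure even if it does not. Subjects already dosed and awaiting culture reduce it further, and the accrual rate is not given.

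The points on size stand, and they keep the priority low. The other two do not defeat the change. The document does not give the secondary aims as a reason to continue past a settled stop, and the Medical Monitor can keep the decision if the deciding failure simply triggers the review.

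Two stronger readings are tempting. A reader of the Statistical Analysis Plan alone might infer that no efficacy stop is possible before 25. The Data Analysis Plans section contradicts that by applying the threshold at 10. A reader might also infer that subjects enrolled late receive a treatment already judged inadequate. The document does not support that either: its stated goal is use with a second agent, and culture-positive subjects are recalled for standard treatment.

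**Conclusion.** The point holds as a minor improvement. The stop at 25 is a fixed failure count, and no section ends enrollment when that count is reached. The mean saving ranges from 0.8–11.2 outcomes at true cure rates of 20–50%, if the line acts only at 25, down to 0.1–1.5 if the 44% rule also acts at 10. Where a value falls in these ranges depends on which of three failure counts applies. The figures rest on independent outcomes with a common cure rate and are upper bounds on the outcomes that could be avoided. Because subjects who are culture-negative at enrollment or do not return are not counted, more than 25 may be dosed to reach 25 outcomes. The fixed look is not invalid, and it does not distort the error rates, which are identical under either approach.

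The conflicts over look timing, the reach of the rule at 10 and the failure count are the larger defect. They must be settled before any curtailment count can be written down.

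**What to change.** First reconcile three items across the four sections: whether the looks are at 25 only or at 10 and 25; whether the efficacy threshold acts at 10; and the failure count (14 implied by 44%, 12 or 11 printed).

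Then add to the Statistical Analysis Plan, Data Analysis Plans and Data Analysis sections:

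*If the number of treatment failures that meets the 25-subject stopping line is reached before 25 outcomes are available, enrollment ends and the data go to the Medical Monitor at that point; subjects already dosed complete their TOC visit and are included.*

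Report the cure rate in all completed subjects and state the sampling rule. Do not add the inverse-sampling estimate of the failure probability, (r − 1)/(n − 1) at the r-th failure in n subjects. It fails if a stop acts at 10. For a 14th failure at outcome 19 it gives 13/18 = 0.72. A trial that passed the look at 10 must then have had exactly 5 failures in the first 10, and the path-count unbiased estimate is C(9,4)/C(10,5) = 126/252 = 0.50. It also does not apply once already-dosed subjects are included.

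The cost is one sentence and a running tally of cultures that are already reported. The downside is that a trial that stops has a few fewer subjects for the cure-rate, renal, pharmacokinetic and MIC results.

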We will evaluate subject's tolerability (Obj. 4) using a standardized symptom questionnaire conducted at the TOC visit. The symptoms questioned will include, but not be limited to, rash, tinnitus, decreased hearing, nausea, vomiting, diarrhea, headaches, and decreased appetite. There will also be a section for free response.

Figure 2: Schematic of Clinical Trial

PK: pharmacokinetics, (i.e. gentamicin peak level); Cr: creatinine, marker of kidney function

Responsibilities

Principle Investigator: [name] MPH
Department of Medicine, Division of Allergy and Infectious Diseases, University of Washington

Study Coordinator: [name]

Study Clinician: TBD

Medical Monitor: [name]
Professor of Medicine, Division of Allergy and Infectious Diseases
University of Washington
Director, UW AIDS Clinical Trials Unit
Associate Director, Center for AIDS Research
University of Washington and Fred Hutch

Study Communication: Harborview Medical Center – STD clinic
[name]
[name]
[contact]
[contact]
Email: [contact]

Study Site: Public Health – Seattle & King County
STD Clinic
[name]
[name]
[contact]

Recruitment and Retention of Subjects

Patients who screen positive for pharyngeal gonorrhea, with or without concomitant GC at other anatomic sites, and have not yet received treatment for this infection or other antibiotics in the past 30 days are eligible for this study. We will not exclude based on gender or HIV status. Recruitment will primarily occur at PHSKC STD Clinic, however, we will also encourage high-diagnosing partner clinics to refer eligible patients as well. We plan to enroll 60 persons with untreated pharyngeal gonorrhea for this study.

Recruitment at PHSKC STD Clinic:

We will employ several strategies to recruit at PHSKC STD Clinic.

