Subjects will be assigned post-injection blood draw at either 30 minutes, 45 minutes or 60 minutes after the gentamicin injection in a sequential fashion, meaning that participant #1 will have a 30 minute draw, #2 a 45 minute and #3 at 60 minute. This one green top tube of blood will be tested for gentamicin concentration as part of Objective 2 and Creatinine.

5. *Counseling:*

The study clinician will counsel the subject to avoid sexual activity, and most specifically performing oral sex, deep kissing, and oral-anal sex until they return for the TOC visit.

Test of Cure Visit

Subjects will return to the PHSKC STD Clinic to meet with the study clinician 4-7 days (+/- 1 day) after their enrollment visit. The study coordinator will call the subject the day prior to the visit as a reminder. At the TOC visit:

1. *Diagnostics:*

The study clinician will obtain a pharyngeal culture for *N. gonorrhoeae* and a blood draw for a follow-up creatinine. (Specimen processing per above). If the culture is positive for *N. gonorrhoeae*, the subject will be called to return for standard of care treatment – Ceftriaxone 250mg IM plus Azithromycin 1g orally once.

2. *Behavior and Symptom screen:*

The study clinician will administer a standardized symptom screening form (see Appendix F) to assess for gentamicin side effects and tolerability. The form will also ask about sexual activity, including kissing, in the time period between treatment and TOC.

Retention Plan

The study coordinator will attempt to schedule the TOC visit at 4 days after the enrollment visit so that if the subject fails to show to that visit, there are still opportunities to reschedule the TOC visit. Additionally, although the subject will be compensated for their time in the study, they will not receive compensation until they return for the TOC visit. This is an incentive for them to keep their follow-up visit.

Data Sources and Data Management

PHSKC STD Clinic Medical Record: We will use gonorrhea test results that occurred prior to enrollment visit from the STD clinic medical record for inclusion criteria. This data will be extracted by chart review during the enrollment visit using subject name and DOB as identifiers. The information will then be entered using a subject ID in the study database. We will also use demographic and sexual behavior data from the medical record.

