APPENDIX E

Study ID: _____

The Gent Study – Enrollment Data Entry Form

Date: _____ Age: _____ Race/ethnicity: _____

Current Gender: Male Female Trans MTF Trans FTM NB/GQ

Sex Assigned at Birth: Male Female

Gender of Sex Partners: Male Female Trans MTF Trans FTM NB/GQ

HIV Status: Positive Negative Number of oral sex partners <2 months: ____

Date of last oral sex exposure: _____

Anatomic Sites of Gonorrhea Infection and Date and Test Type:

Pharynx: Test Date: _____ **NAAT** Yes No **Culture** Yes No

NAAT Type: _____

Rectum: Test Date: _____ **NAAT** Yes No **Culture** Yes No

NAAT Type: _____

Urethra: Test Date: _____ **NAAT** Yes No **Culture** Yes No

NAAT Type: _____

Cervix/Vagina: Test Date: _____ **NAAT** Yes No **Culture** Yes No

NAAT Type: _____

Height: _____ cm

Weight: _____ kg

Medical History:

Current Medications (and doses): _____

Date & Time of Administration of Gentamicin: _____

Date & Time of Blood Draw for Gent PK and Cr: _____

Immediate reactions (if any):

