APPENDIX F

Study ID: _____

The Gent Study – TOC Visit Data Entry Form

TOC Visit Date: _____ Days since Tx: _____

Symptoms since Tx:

Y or N Headache (if yes, characterize): _____

Y or N Vision Changes (if yes, characterize): _____

Y or N Changes in Hearing (if yes, characterize): _____

Y or N Tinnitus (if yes, characterize): _____

Y or N Urinary Symptoms (if yes, characterize): _____

Y or N Nausea or Vomiting (if yes, characterize): _____

Y or N Diarrhea (if yes, characterize): _____

Y or N Constipation (if yes, characterize): _____

Y or N Rash (if yes, characterize): _____

Y or N Other (if yes, characterize): _____

Sexual Activity Since Treatment:

1) Have you been intimate with any partners since treatment? Y or N
(*Intimacy includes kissing, oral-anal sex, oral-penile sex, anal-penile sex, penile-vaginal sex*)

2) Were any of your partners since treatment the same as someone you were intimate with in the 2 months prior to your pharyngeal gonorrhea diagnosis? Y or N

If Yes to #1 above, ask the following questions:

3) How many days did you deep kiss a partner since treatment? _____

4) How many partners did you deep kiss since treatment? _____

5) How many times did you perform oral sex on a penis since treatment? _____

- 6) How many male-bodied persons did you give oral sex to since treatment? _____
- 7) How many times did you rim a partner since treatment? _____
- 8) How many partners did you rim since treatment? _____
- 9) How many times did you top (i.e. insertive anal intercourse) a partner since treatment?

- 10) How many partners did you top since treatment? _____
- 11) How many times did you bottom (i.e. have receptive anal intercourse) for a partner since treatment? _____
- 12) For how many partners did you bottom since treatment? _____
- 13) How many times did you have vaginal sex with a partner since treatment? _____
- 14) How many partners did you have vaginal sex with since treatment? _____

TOC Testing Conducted and Results:

Pharynx: NAAT Result Positive Negative

Culture Done Yes No

Culture Results Positive Negative

AST results (in mcg/mL): PCN: _____ TET: _____ CIP: _____

CFX: _____ CTX: _____ AZM: _____ GENT: _____

Rectum: NAAT Result Positive Negative

Culture Done Yes No

Culture Results Positive Negative

AST results (in mcg/mL): PCN: _____ TET: _____ CIP: _____

CFX: _____ CTX: _____ AZM: _____ GENT: _____

Urethra: NAAT Result Positive Negative

Culture Done Yes No

Culture Results Positive Negative

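### Apart from hearing loss and tinnitus, no symptoms are recorded before the injection, so complaints already present may enter the side-effect proportion and bias it upward

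*Combined protocol and SAP*

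**What the plan says.** Tolerability is part of the second specific aim. The Statistical Analysis Plan section describes the result in one sentence: "we will report the number and proportion of subjects who report side effects". It then says that tolerability will be evaluated "using a standardized symptom questionnaire conducted at the TOC visit", and the Analyses section repeats this in substance. Under Test of Cure Visit, the study clinician gives the form "to assess for gentamicin side effects and tolerability". The Data Safety and Monitoring Plan uses the same source for adverse events: "AEs are identified at the TOC visit using the symptom screen, and with Creatinine monitoring".

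The form is Appendix F. Its symptom block is headed "Symptoms since Tx" and consists of yes/no items, each with a line to characterize a positive answer. One of them is "Y or N Urinary Symptoms (if yes, characterize)"; diarrhea and constipation are also listed.

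On eligibility, Recruitment and Retention of Subjects admits patients "with or without concomitant GC at other anatomic sites". On the enrollment form, Appendix E, the only field for symptoms is "Immediate reactions (if any)", placed after the times of dosing and blood draw.

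**The concern.** In a study without a control group, each subject's own pre-dose state is the only available reference for symptoms. The plan uses that reference for creatinine and, among treatment failures, for MIC. It does not use it for symptoms, with two exceptions. A subject who had a listed complaint before the injection and still has it at TOC can truthfully answer yes to a question about symptoms since treatment. If that answer goes into the reported proportion, the study overstates how often 360 mg causes side effects. The overlap is plausible here because subjects with gonorrhea at other sites are eligible and the form asks about urinary symptoms.

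What is at stake is the interpretation of the tolerability half of Aim 2. The cure rate, creatinine, drug-level and MIC results do not depend on it.

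**Working it through.** The documents state no expected side-effect rate, background symptom rate or precision for tolerability, so there is no figure of theirs to reproduce. The check has two parts.

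**1. Is symptom status recorded anywhere before the injection?**

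- *Appendix D (screening):* asks about a history of hearing loss or tinnitus; either excludes the patient. These two TOC items therefore have a known negative history at entry. No other TOC symptom is asked.
- *Intake & Data Entry Form, and Appendix E:* demographics, HIV status, infected sites, height, weight, medications and medical history. There is no list of current symptoms, and the reactions field follows dosing.
- *Data Sources and Data Management:* the medical record supplies gonorrhea results, demographics and sexual behavior. The list of data points names symptoms only after treatment.
- *Appendix F:* has no field for date of onset or for presence before dosing.
- *Statistical Analysis Plan and Analyses sections:* no restriction to new or worsened symptoms, and no mention of attribution.

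So, apart from hearing loss and tinnitus, a persisting complaint cannot be told from a new one using the planned fields, unless the free-text line happens to say so.

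**2. How large could the effect be? (illustration only)**

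Inputs: N = 60 is the planned sample size, and all 60 are assumed to return for TOC. Two rates are assumed because the documents give neither:

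- *b*: the proportion with a listed symptom that is present before dosing, persists, and is reported at TOC.
- *d*: the proportion with a drug-caused symptom, taken as independent of *b*.

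Expected crude proportion = 1 − (1 − d)(1 − b).

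With no drug effect (d = 0) this reduces to b, and the expected count is 60 × b:

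| b | Subjects counted | Exact 95% CI for that count out of 60 |
|---|---|---|
| 5% | 3 | 1.0% to 13.9% |
| 10% | 6 | 3.8% to 20.5% |
| 20% | 12 | 10.8% to 32.3% |
| 30% | 18 | 18.8% to 43.2% |

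With a real drug effect:

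| b | Crude proportion, d = 5% | Crude proportion, d = 10% |
|---|---|---|
| 5% | 1 − 0.95 × 0.95 = 9.8% | 1 − 0.90 × 0.95 = 14.5% |
| 10% | 1 − 0.95 × 0.90 = 14.5% | 1 − 0.90 × 0.90 = 19% |
| 20% | 1 − 0.95 × 0.80 = 24.0% | 1 − 0.90 × 0.80 = 28% |
| 30% | 1 − 0.95 × 0.70 = 33.5% | 1 − 0.90 × 0.70 = 37% |

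If d and b are equal, the crude figure is nearly double the drug-caused rate. The confidence interval gives no warning of this, because it describes sampling error around the inflated proportion.

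**The case against.** The strongest reply is that the plan nowhere says every positive answer on Appendix F is a side effect. A clinician gives the form, each item has a line for detail, infected sites are known from enrollment, and the adverse-event section has an attribution scale with a category for events that another cause explains better or whose timing does not fit. Persisting dysuria in a subject with known urethral gonorrhea is the sort of case that category could hold. This stands as far as it goes: the documents support saying that such complaints may be counted, not that they will be. It does not close the gap. No section applies attribution to the reported proportion, the adverse-event definition itself disregards relatedness, and a judgment about timing needs onset information that no form collects.

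Several other points also stand. Hearing loss, which the Medical Monitor reviews in real time, and tinnitus do have a baseline. The Executive Summary gives 91% efficacy for genital infection, and concurrent chlamydia and syphilis are excluded, so symptoms from a urethral infection may often be resolving by TOC. The documents do not tie diarrhea or constipation to rectal infection, so that overlap is only a possibility. An all-causality count is consistent with the protocol's own adverse-event definition, and the error, if any, overstates harm in a descriptive secondary result.

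A reader might also infer that inflated symptom counts could stop the study, because the monitoring plan names adverse events among its stopping rules. The documents do not support that. The only adverse-event threshold they put a number on is a creatinine increase above 40% in a stated share of subjects, and symptom answers do not enter it.

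**Conclusion.** The concern holds in this limited form. Hearing loss and tinnitus aside, the plan records no symptom status before the injection, has no comparator, and reports a crude proportion with no new-or-worse rule and no stated use of attribution. Pre-existing complaints may therefore enter the side-effect figure, and the bias from this runs upward.

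Its size cannot be found from the documents. The range of 3 to 18 of 60 rests on assumed rates of 5% to 30% for persisting symptoms, on all 60 subjects returning, and on none of these complaints being removed by attribution. It shows what the design would allow and is not an estimate. This is an inexpensive improvement to a secondary aim.

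**What to change.** Add the Appendix F symptom list to Appendix E as a block completed before the injection. In the Statistical Analysis Plan and Analyses sections, define the main tolerability result as the number and proportion of subjects with any symptom that is new, or worse, at TOC compared with the pre-dose entry. Report the all-symptoms count beside it, so that no safety information is lost. Appendix F then needs a way to mark a symptom as worse than before, and the text should say whether the attribution scale plays any part in the reported proportion.

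The cost is one more form block and about a minute at a visit that already takes place, with no new procedure or staff. The change removes complaints that were present before dosing and have not worsened. It does not remove unrelated complaints that first arise between dosing and TOC, which a single-arm study cannot separate from drug effects; the report should say so.
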